14.3. Analysis Populations

Safety Population:

All subjects who were administered any test article excluding subjects who drop out prior to administering any test article. At least one observation should be recorded.

Clinical Study Protocol

Johnson & Johnson Vision Care, Inc.

Per-Protocol Population:

All subjects who have successfully completed all visits and did not substantially deviate from the protocol as determined by the trial cohort review committee prior to database hard lock (Per-Protocol Population). Justification of excluding subjects with protocol deviations in the per-protocol population set will be documented in a memo to file.

Intent-to-Treat (ITT) Population:

All randomized subjects regardless of actual treatment and subsequent withdrawal from study or deviation from protocol. At least one observation should be recorded.

14.4. Level of Statistical Significance

All planned analysis for this study will be conducted with an overall type I error rate of 5%. No adjustment for multiple comparisons will be conducted unless specified otherwise.

14.5. Primary Analysis

The co-primary endpoints for this study are the CLUE comfort and the CLUE vision scores evaluated after 7 ± 2 days of lens wear. The primary analysis will be conducted on per-protocol and ITT populations.

CLUE Comfort and Vision scores

CLUE comfort and vision scores after 7 ± 2 days of lens wear will be analyzed separately using a linear mixed effect model to compare between Test and Control lenses. Each regression model will include the baseline score, lens type, lens wearing sequence and lens wearing period as fixed effects and investigational site as a random effect (G-side). Other subject characteristics such as habitual lens, age, gender and will also be included as fixed effects when appropriate. The habitual lens will be categorized as ACUVUE OASYS 1-DAY, silicone hydrogel daily disposable – non-ACUVUE OASYS 1-DAY and non-silicone hydrogel daily disposable. The covariance of residual errors between different periods for the same subject will be modeled using either homogenous compound symmetry (CS), First-Order Ante-dependence (ANTE) or unstructured (UN) covariance structure. The structure that returns the lowest finite sample corrected Akaike's Information criterion⁷ will be selected as the structure that best fits the model. The Kenward and Roger method will be used for the calculation of the denominator degree of freedom.⁸

The null and alternative hypotheses for non-inferiority of Test lens relative to Control are as follows:

$$H_0: \Delta < -5$$
$$H_A: \Delta \geq -5$$

where Δ is the CLUE score mean difference after 7 ± 2 days of lens wear between Test lens and Control lens (Test minus Control). The hypothesis will be tested via the corresponding two-sided 95% confidence interval (CI) for least squares mean (LSM) difference (Test - Control) in CLUE scores. Non-inferiority will be declared if the lower bound of the confidence interval

Clinical Study Protocol

Johnson & Johnson Vision Care, Inc.

of the mean difference between Test and Control is greater than -5. If non-inferiority is demonstrated, superiority will be tested and concluded if the lower bound of the 95% CI is greater than 0.

14.6. Secondary Analysis

Visual Performance

Monocular distance visual performance in logMAR scale will be analyzed using a linear mixed effect model to compare between Test and Control lenses. The regression model will include baseline scores, lens type, lens wearing sequence and lens wearing period as fixed effects; and investigational site and patient as random effects. Other subject characteristics such as habitual lens as defined in the primary analysis, age, gender and will also be included as fixed effects when appropriate. The covariance of residual errors between different periods for the same eye and subject across wearing periods will be modeled using either homogenous compound symmetry (CS) , First-Order Ante-dependence (ANTE), or unstructured (UN) covariance structure. The structure that returns the lowest finite sample corrected Akaike's Information criterion⁷

The null and alternative hypotheses for non-inferiority of Test lens relative to Control are as follows:

$$\begin{aligned} H0: \Delta &> 0.05 \\ HA: \Delta &\leq 0.05 \end{aligned}$$

where Δ is the mean difference in logMAR between Test lens and Control lens (Test minus Control). Non-inferiority will be declared if the upper bound of the confidence interval of the mean difference between Test and Control is less than 0.05.

Average Daily Wearing Time

Average daily wear time will be analyzed using the same linear mixed effect model described in the primary analysis.

The null and alternative hypotheses for non-inferiority of Test lens relative to Control are as follows:

$$\begin{aligned} H0: \Delta &< -1 \\ HA: \Delta &\geq -1 \end{aligned}$$

where Δ is the mean difference in average daily wearing time between Test lens and Control lens (Test minus Control). Non-inferiority will be declared if the lower bound of the confidence interval of the mean difference between Test and Control is greater than -1.

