4. STUDY DESIGN AND RATIONALE

4.1. Description of Study Design

This study is a multi-site, randomized, double-masked, 2×2 crossover design, 1-week dispensing study. Subjects will wear bilaterally both Test and Control lenses in a random order for 1-week each as a daily disposable modality with a wash-out period of 1 week between the wearing periods.

Period 1:

At study Visit 1, subjects will be consented and screened for inclusion/exclusion criteria. If a subject is found to meet all eligibility criteria (see Section 3.4.), they will be randomly assigned to either Test/Control or Control/Test sequence using 1:1 ratio (i.e. 1/2 of subjects on the Test/Control sequence and 1/2 on the Control/Test sequence). Subjects will fit the first pair of lenses in both eyes based on the sequence assigned; otherwise, the subject will be deemed ineligible for this study. Subjects will be advised to wear the study lenses at least 8 hours a day for a minimum of 5 days.

Successfully dispensed subjects at the Visit 1 will be scheduled for a follow-up visit (Visit 2). The follow-up visit will occur approximately 7 ± 2 days after the Visit 1. Unscheduled follow-up visits may occur during the study. At this visit, CLUE comfort and vision, slit lamp findings will be captured.

Wash-out period:

After completion of Visit 2, there is a 7 to 9 days washout period during which subjects may use their habitual products.

Period 2:

Following the washout period, the subject returns for Visit 3 and post-washout baseline evaluation will take place prior to lens fitting. After baseline evaluation, subject will be fitted and dispensed with the second pair of lenses in the assigned sequence. Subjects will be advised to wear the study lenses at least 8 hours a day for a minimum of 5 days.

Visit 4 takes place 7 ± 2 days after Visit 3, at which CLUE comfort and vision, slit lamp findings, final evaluation will take place.

Both study lenses will be worn as a daily disposable modality. JJVC will provide the investigational sites with sufficient quantities of study lenses and supplies to complete the study.

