5. TEST ARTICLE ALLOCATION AND MASKING

5.1. Test Article Allocation

The study lenses will be worn in a bilateral and random fashion using a 2×2 crossover design. A computer-generated randomization scheme will be used to randomly assign subjects, in block of 2, to one of the two possible lens wear sequences: Test/Control or Control/Lens. The random scheme will be generated using the PROC PLAN procedure from Statistical Analysis System (SAS) Software Version 9.4 or higher (SAS Institute, Cary, NC).⁶

The study site must follow the randomization scheme provided and complete enrollment per the randomization list and not pre-select or assign subjects. The randomized assignment of subjects will be performed at the first visit prior to the first fitting. The following must have occurred prior to randomization:

- Informed consent has been obtained
- Subject meets all the inclusion / exclusion criteria
- Subject history and baseline information has been collected.

Clinical Study Protocol

Johnson & Johnson Vision Care, Inc.

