7.2. Detailed Study Procedures

VISIT 1

Screening Visit, Baseline Evaluation, Dispensing Visit.

Subjects should attend wearing their habitual lenses.

Visit 1: Screening		
Step	Procedure	Details
1.1	Statement of Informed Consent	
Each subject must read, understand, and sign the Statement of Informed Consent before being enrolled into the study. The Principal Investigator or his/her designee conducting the informed consent discussion must also sign the consent form.
 
Note: The subject must be provided a signed copy of this document.

1.2	Demographics	Record the subject's year of birth, gender, race and ethnicity.
1.3	Medical History and Concomitant Medications	Questions regarding the subjects' medical history and concomitant medications.
1.4	Habitual Lenses	Questions regarding the subject's habitual lens type, parameters, and duration
1.5	Contact lens wear times	Record the current wear time (WT) and comfortable wear time (CWT).
1.6	Eligibility after Screening	
All responses to Inclusion Criteria questions must be answered "yes" and all responses to Exclusion Criteria questions must be answered "no" for the subject to be considered eligible.
 
If subject is deemed to be ineligible after screening, proceed to Final Evaluation and complete all forms.

Visit 1: Baseline		
Step	Procedure	Details
1.7	Background CLUE Questionnaire	Subject will complete questions regarding their experiences with their habitual lenses.
1.8	Subject-reported Ocular Symptoms	Subject Reported Ocular Symptoms and Problems
1.9	Distance visual acuity (VA)	Record the distance Snellen VA for OD, OS and OU. Subject must keep reading smaller lines until less than half the letters are correctly identified.

Clinical Study Protocol
Johnson & Johnson Vision Care, Inc.

Visit 1: Baseline		
Step	Procedure	Details
1.10	Remove habitual lenses	The subject's habitual lenses will be removed and stored in their own lens case. If they forgot to bring their lens case, one will be provided to them.
1.11	Subjective spherocylinder refraction and VA	Perform binocular subjective best spherocylinder refraction and record the best corrected Snellen VA for OD, OS and OU.

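### The logMAR model in section 14.6 has no term for variation the two eyes share within a period, so its interval is too narrow if their lens differences correlate positively

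*Combined protocol and SAP*

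**What the plan says.** Section 14.6 (Visual Performance) fits a linear mixed model to monocular logMAR, and section 14.1 confirms that eye-level results are used. The fixed effects are a baseline score, lens type, sequence and period, with further subject characteristics where appropriate. The random effects are "investigational site and patient as random effects". On the residuals the section says: "The covariance of residual errors between different periods for the same eye and subject across wearing periods will be modeled", with compound symmetry (CS), first-order ante-dependence (ANTE) and unstructured (UN) as candidates. Non-inferiority is declared if the upper confidence bound for Test minus Control lies below 0.05 logMAR.

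The design is a 2×2 crossover with the same lens type on both eyes. Section 4.1 states: "Subjects will wear bilaterally both Test and Control lenses in a random order for 1-week each". In section 7.2 both eyes are tested at the same follow-up visit (steps 2.7 and 4.7).

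Neither section 14.6 nor any other section names a patient-by-period term or a covariance between the two eyes in the same period.

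**The concern.** Each patient gives two eye-level Test-minus-Control differences. They come from the same pair of visits and lens types, with the same examiner conditions and the same subject state on the day. Anything that moves both eyes together at one visit makes these differences correlate, and two eyes then carry less information than two independent observations.

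A patient intercept does not capture this. It is the same in both periods and drops out of the difference. Site drops out for the same reason. A residual covariance confined to one eye across periods does not link the eyes either. The standard error of the lens effect can therefore be understated and the 0.05 logMAR test made too easy to pass. Section 14.2 says the data will be used to design future trials, so an understated error could also be carried forward.

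**Working it through.** **Plan's own figure.** None exists to reproduce: the documents give no logMAR SD, correlation, power or sample size calculation.

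**Inputs from the documents.** 120 completers, 60 per sequence (section 4.3, Table 1), hence 240 eyes; margin 0.05 logMAR (sections 2.3 and 14.6); 5% overall type I error (section 14.4).

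**Assumptions.**
- rho, the correlation between the two eyes' lens differences: 0.1 to 0.5.
- SD of one eye's lens difference: 0.10 or 0.14 logMAR, needed only in steps 4 and 5.
- A two-sided 95% interval, because section 14.6 states no level.
- One value per eye per period, and complete data.

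**Step 1: what the listed structures allow.** With a residual block of two periods within an eye, ANTE and UN are the same 2×2 matrix. None of the three structures puts any covariance between the eyes. The patient variance enters all four between-eye covariances equally, so its contribution to cov(d_OD, d_OS) is s − s − s + s = 0.

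**Step 2: standard error.** Let each eye's difference have variance v.
- True variance of the lens effect: v(1+rho)/(2n), with n = 120.
- Variance under the model: v/(2n).
- True SE / model SE = sqrt(1+rho), whatever the SD.

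**Step 3: error and coverage.** One-sided error at a true loss of exactly 0.05 is 1 − Φ(1.96/sqrt(1+rho)). Coverage is 1 minus twice that.

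| rho | sqrt(1+rho) | interval too narrow by | one-sided error | coverage |
|---|---|---|---|---|
| −0.2 | 0.894 | (11.8% too wide) | 1.4% | 97.2% |
| 0 | 1.000 | 0 | 2.5% | 95.0% |
| 0.1 | 1.049 | 4.7% | 3.1% | 93.8% |
| 0.3 | 1.140 | 12.3% | 4.3% | 91.4% |
| 0.5 | 1.225 | 18.4% | 5.5% | 89.0% |

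A REML simulation (2,000 crossovers per setting, 60 per sequence, two eyes, site omitted because it is constant within a subject) agrees. One-sided error with the same-eye models was 2.8–3.4%, 3.9–4.7% and 5.7–5.8% at rho 0.1, 0.3 and 0.5. With a patient-by-period effect added it was 2.0–2.8% in all eight settings, which included rho = 0. The Monte Carlo SE is about 0.25–0.35 points.

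**Step 4: when the verdict changes.** Model half-width = 1.96 × SD/sqrt(240); the corrected one is that times sqrt(1+rho). At rho 0.5:
- SD 0.10: 0.0127 becomes 0.0155. The verdict changes only for estimates between 0.05 − 0.0155 = 0.0345 and 0.05 − 0.0127 = 0.0373.
- SD 0.14: 0.0177 becomes 0.0217. The window is 0.0283 to 0.0323.

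**Step 5: how often.** The chance that the estimate falls in that window, with true SE = SD × sqrt(1.5)/sqrt(240) = 0.0079 or 0.0111, is:
- at zero true difference: about 0.0005% (SD 0.10) or 0.35% (SD 0.14);
- at a true loss of 0.02: about 2% or 9%.

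**The case against.** The strongest reply is that this hardly matters. Section 2.3 calls all hypotheses exploratory, the endpoint is secondary, rho and the SD are assumed, and the lenses differ only in manufacturing technology. Near equivalence the verdict would almost never flip, as step 5 shows. All of that stands, and it limits the weight of the point. It does not make the stated interval right when rho is positive, which is plausible with the same lens type and visit for both eyes but is not documented.

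A reader might infer that section 14.6 supports two equally good readings, one with a residual block per eye and one with a joint 4×4 eye-by-period block per subject, so that two analysts following it would disagree. The text does not bear this out. It keeps a patient random effect. Beside a 4×4 UN block that variance is not identifiable, and beside a 4×4 CS block it is redundant. The same-eye block is the one that fits the patient effect under all three structures. The issue is one missing term.

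A reader might also look for bias in the baseline covariate, which section 14.6 does not define for logMAR. Acuity before fitting is recorded by eye (section 7.2, steps 1.9, 1.11 and 3.5), so a baseline exists. Which one is meant is missing detail, and no bias follows from it.

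**Conclusion.** The point holds, with limited consequence. As naturally read, the logMAR model treats the two eyes' lens differences as independent and understates the standard error by sqrt(1+rho) when they correlate positively. This factor is exact for complete, balanced data with one value per eye per period and does not depend on the SD. How large rho is cannot be learned from the documents. The half-widths and verdict windows also rest on the assumed SDs.

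It would go too far to infer that the logMAR conclusion will be wrong or that the primary objective is at risk. The verdict changes only in a narrow range of estimates, and each CLUE endpoint has one score per subject and period, so the issue does not arise there.

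**What to change.** In section 14.6, add a patient-by-period random effect to the logMAR model, alongside the patient effect and the same-eye covariance across periods. In a 2×2 crossover this is the same as patient-by-lens.

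An alternative is a single unstructured 4×4 eye-by-period matrix per subject. In that case remove the patient random effect, which would otherwise overparameterise the model, and use one value per eye per period for each lighting condition. Section 7.2 takes two readings under each of two conditions, and a 4×4 matrix is undefined if these enter as separate rows.

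The cost is wording only, with no new data. Against the current model the interval widens by sqrt(1+rho): about 5% at rho 0.1, 14% at 0.3 and 22% at 0.5. Power at zero true difference stays above 99% for both assumed SDs. The lowest value, at SD 0.14 and rho 0.5, is Φ((0.05 − 0.0217)/0.0111), about 99.5%.

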14.7. Other Exploratory Analyses

A subgroup analysis will be conducted by considering only subjects who are habitual users of ACUVUE OASYS 1-DAY.

Clinical Study Protocol

Johnson & Johnson Vision Care, Inc.

14.8. Interim Analysis

No interim analysis is planned.

14.9. Procedure for Handling Missing Data and Drop-Outs

Missing or spurious values will not be imputed. The count of missing values will be included in the summary tables and listings.

Subject dropout is expected to be one of the main reasons of missing data in this clinical trial. Past clinical trials don't provide the evidence that subject dropout is systematic or not-at-random. To evaluate the impact of missing data, sensitivity analysis will be conducted using multiple imputation methods if the proportion of subject dropout is greater than the 15%. The SAS/STAT procedures PROC MI and PROC MIANALYZE will be utilized with a parametric regression method used to make at least 15 imputations.

14.10. Procedure for Reporting Deviations from Statistical Plan

The analysis will be conducted according to that specified in above sections. There are no known reasons for which it is planned to deviate from these analysis methods. If for any reason a change is made, the change will be documented in the study report along with a justification for the change.

15. DATA HANDLING AND RECORD KEEPING/ARCHIVING

15.1. Electronic Case Report Form/Data Collection

The data for this study will be captured on electronic case report forms (eCRFs) using an EDC system Bioclinica. An authorized data originator will enter study data into the eCRFs using the EDC system. Data collected on equipment that is not captured in EDC will be formatted to the specification of the JJVC database manager and sent to JJVC for analysis.

External Data Sources for this study include: Not Applicable

The clinical data will be recorded on dedicated eCRFs specifically designed to match the study procedures for each visit. Only specifically delegated staff can enter data on a CRF. Once completed, the eCRFs will be reviewed for accuracy and completeness and signed by the Investigator. The sponsor or sponsor's representatives will be authorized to gain access to the subject recordation for the purposes of monitoring and auditing the study.

Edit checks, electronic queries, and audit trails are built into the system to ensure accurate and complete data collection. Data will be transmitted from the clinical site to a secure central database as forms are completed or updated, ensuring information accuracy, security, and confidentiality. After the final database lock, the Investigator will be provided with Individual Patient Profiles (IPP) including the full audit trail on electronic media in PDF format for all of the study data. The IPP must be retained in the study files as a certified copy of the source data for the study.

Clinical Study Protocol

Johnson & Johnson Vision Care, Inc.

The content and structure of the eCRFs are compliant with ISO14155:2011.¹

15.2. Subject Record

At a minimum, subject record should be available for the following:

- subject identification
- eligibility
- study identification
- study discussion
- provision of and date of informed consent
- visit dates
- results of safety and efficacy parameters as required by the protocol
- a record of all adverse events
- follow-up of adverse events
- medical history and concomitant medication
- test article receipt/dispensing/return records
- date of study completion
- reason for early discontinuation of test article or withdrawal from the study, if applicable

The subject record is the eCRF or an external record. The author of an entry in the subject record must be identifiable. The first point of entry is considered to be the source record.

Adverse event notes must be reviewed and initialed by the Investigator.

15.3ClinicalTrials.gov

This study will be registered on ClinicalTrials.gov by the Sponsor.

16. DATA MANAGEMENT

16.1. Access to Source Data/Document

The Investigator/Institution will permit trial-related monitoring, audits, IEC/IRB review and regulatory inspection(s) by providing direct access to source data/documents. Should the clinical site be contacted for an audit by an IEC/IRB or regulatory authority, JJVC must be contacted and notified in writing within 24 hours.

16.2. Confidentiality of Information

Information concerning the investigational product and patent application processes, scientific data or other pertinent information is confidential and remains the property of JJVC. The Investigator may use this information for the purposes of the study only. It is understood by the Investigator that JJVC will use information developed in this clinical study in connection with the development of the investigational product and therefore may disclose it as required to other clinical investigators and to regulatory agencies. In order to allow the use of the information derived from this clinical study, the Investigator understands that he/she has an

Clinical Study Protocol

Johnson & Johnson Vision Care, Inc.

obligation to provide complete test results and all data developed during this study to the Sponsor.

16.3. Data Quality Assurance

Steps will be taken to ensure the accuracy and reliability of data, include the selection of qualified investigators and appropriate clinical sites and review of protocol procedures with the Principal Investigator. The Principal Investigator, in turn, must ensure that all Sub-Investigators and clinical site personnel are familiar with the protocol and all study-specific procedures and have appropriate knowledge of the study article.

Training on case report form completion will be provided to clinical site personnel before the start of the study. The Sponsor will review case report forms for accuracy and completeness remotely during the conduct of the study, during monitoring visits, and after transmission to data management. Any data discrepancies will be resolved with the Investigator or designee, as appropriate.

Quality Assurance representatives from JJVC may visit clinical sites to review data produced during the study and to access compliance with applicable regulations pertaining to the conduct of clinical trials. The clinical sites will provide direct access to study-related source data/documents and reports for the purpose of monitoring and auditing by JJVC and for inspection by local and regulatory authorities.

